5.2 Discussion of Study Design

Once subjects have successfully completed the 4-week Screening Period, a total of 420 subjects will be randomized in a 1:1:1 ratio (140 subjects per treatment group) to 1 of 3 treatment groups as follows:

1. OKZ 64 mg q4w: SC injection of OKZ 64 mg q4w (alternating with SC injection of placebo OKZ q4w to maintain blinding) + MTX.
2. OKZ 64 mg q2w: SC injection of OKZ 64 mg q2w + MTX.
3. Placebo: SC injection of placebo q2w + MTX.

This is a double-blind study; as the placebo differs in appearance from OKZ, study treatment will be prepared by an independent unblinded pharmacist or designee (e.g., nurse) and provided to blinded site staff in blinded syringes that are identical in appearance. The SC injections of OKZ and placebo will be administered every other week by blinded trained study staff. As noted above for treatment group No. 1, in order to maintain the blind, subjects randomized to receive OKZ q4w will receive placebo injections at the alternate q4w interval (e.g., Week 2, Week 6, etc.) at prespecified visits as described in Table 1 or Table 2 (as applicable).

Throughout the double-blind Treatment Period, all subjects will be required to remain on a stable dose of background MTX at 15 to 25 mg/week (or ≥ 10 mg/week if there is documented intolerance to higher doses) with a stable route of administration, and concomitant treatment with folic acid ≥ 5 mg per week or equivalent is required for all subjects. From Week 0 through Week 24, subjects will return to the study site at least every other week for response and safety assessments as per Table 1 or Table 2 (as applicable). Blood samples to assess OKZ concentrations in plasma will be collected periodically during the Treatment Period as per Table 5.

Subjects will be classified in terms of their response to study treatment at Week 14, with nonresponders defined as subjects from any treatment group who do not improve by at least 20% in both SJC and TJC (66-68 joint assessment). Starting at or as close as possible to Week 14, nonresponders in all groups will be administered sulfasalazine and/or hydroxychloroquine as rescue medication in addition to their assigned treatment (see Section 6.13.3).

The last dose of study treatment (OKZ or placebo) will take place at Week 22.

After completion of the 24-week double-blind Treatment Period, subjects will be offered the opportunity to enter the long-term OLE study. Subjects who do not consent to participate in

the OLE study will come to the EoT Visit 2 weeks after the last dose of the study treatment for scheduled assessments, after which they will then enter the Safety Follow-Up Period. During the Safety Follow-Up Period, subjects will return for visits +4, +8, and +22 weeks after the last dose of study treatment at Week 22 as per Table 1 or Table 2 (as applicable) (Visits SFU-1 [Week 26], SFU-2 [Week 30], and SFU-3 [Week 44], respectively).

Subjects who discontinue randomized study treatment early will adhere to the double-blind Treatment Period visit schedule outlined in Table 1 or Table 2 (as applicable), as if they were still receiving study treatment. In addition, all subjects who discontinue study treatment early will be required to attend the EoT Visit +2 weeks after the last dose of study treatment, as well as extended Safety Follow-Up assessments +4 weeks (Visit SFU-1), +8 weeks (Visit SFU-2), and +22 weeks (Visit SFU-3) after the last dose of study treatment.

Adverse events will be assessed throughout the study period and evaluated using the CTCAE version 4.0.

There will be ongoing monitoring of safety events, including laboratory findings, by R-Pharm and R-Pharm's designee. In addition, safety will be assessed throughout the study by an independent Data Safety Monitoring Board (DSMB) (see Section 7.6.4 for further details).

5.2.1 Cardiovascular Risk Assessment

The RA population is known to have an increased risk of CV events. In order to fully assess the CV risks associated with OKZ, the following approach will be used:

1. Potential major adverse cardiac events (MACE) will be adjudicated by an independent Cardiovascular Adjudication Committee (CVAC) according to a predefined charter. The charter will define the criteria, data, and source documentation required to adjudicate all MACE.
2. Baseline CV risks including individual risk factors (e.g., tobacco use, presence of hypertension, diabetes mellitus, and lipid profile) will be assessed.
3. Known CV risk factors will be monitored and assessed to detect any trends over long-term exposure.

Cardiovascular risk assessment data will be provided to the CVAC for use in review and adjudication of MACE (see Section 7.6.4.2).

5.2.2 Safety Follow-up Assessments

Given the long half-life of OKZ (approximately 31 days), all subjects will be followed up for approximately 5 OKZ half-lives (i.e., 22 weeks) after the final dose of study treatment.

For subjects remaining on randomized therapy until the last scheduled dose of study treatment at Visit 14 (Week 22) and not entering the OLE study, a full safety assessment will be performed at the EoT Visit (Visit 15 [Week 24]) and extended Safety Follow-Up procedures will be performed at visits scheduled +4, +12, and +22 weeks after the last dose of study treatment (i.e., Visits SFU-1 [Week 26], SFU-2 [Week 30], and SFU-3 [Week 44], respectively).

Subjects who discontinue randomized study treatment early (i.e., prior to Week 24) will adhere to the established double-blind Treatment Period visit schedule outlined in Table 1 or Table 2 (as applicable), as if they were still receiving study treatment. In addition, all subjects who discontinue study treatment early will have extended Safety Follow-Up assessments performed at the following time points:

- Full safety assessment 2 weeks after the last dose of study treatment (EoT Visit) (see Section 5.4.2)
- Safety Follow-Up Visit +4 weeks after the last dose of study treatment (Visit SFU-1) (see Section 5.4.3.1)
- Safety Follow-Up Visit +12 weeks after the last dose of study treatment (Visit SFU-2) (see Section 5.4.3.2)
- Safety Follow-Up Visit +22 weeks after the last dose of study treatment (Visit SFU-3) (see Section 5.4.3.3)

Depending on the timing of study treatment discontinuation, it is possible that the double-blind Treatment Period visits (Visits 2 through 15) may occur at the same time as the Safety Follow-Up Visits. In such cases, the study site staff should complete all study procedures required by both visits; if there are overlaps in the required laboratory tests, however, only one set of tests will be performed.

All subjects will be reminded of study contact information to report potential SAEs and are to inform the Investigator if they experience such events during the Safety Follow-Up Period.

5.3 Selection of Study Population

The study population will consist of a representative group of subjects of at least 18 years of age, fulfilling ACR 2010 revised classification criteria for RA for at least 12 weeks prior to

Screening. Eligible subjects are required to have active RA defined as ≥ 6 tender joints out of 68 and ≥ 6 swollen joints out of 66 at Screening and baseline, in combination with CRP above the upper limit of normal (ULN) at Screening. Subjects must have been on background MTX treatment at 15 to 25 mg/week (or ≥ 10 mg/week if there is documented intolerance to higher doses) for at least 12 weeks prior to Screening with a stable dose and route of administration for at least 6 weeks prior to Screening and have experienced an inadequate response (see Section 5.1 for definition of inadequate response to MTX) to treatment. Subjects will be maintained on a stable dose of MTX therapy throughout the study, and concomitant treatment with folic acid ≥ 5 mg per week or equivalent will be required for all subjects.

This is an international study and it is expected that subjects will be enrolled at approximately 50 sites across 4 countries. A total of 420 subjects will be randomized. Enrollment will stop as soon as the target number of randomized subjects is reached.

5.3.1 Inclusion Criteria

Subjects may be enrolled in the study only if they meet all of the following criteria:

1. Male or female subjects ≥ 18 years of age
2. Subjects willing and able to sign informed consent
3. Subjects must have a diagnosis of adult-onset RA classified by ACR/EULAR 2010 revised classification criteria for RA (Aletaha et al, 2010) for at least 12 weeks prior to Screening.
 - If the subject was diagnosed according to ACR 1987 criteria previously, the Investigator may classify the subject per ACR 2010 retrospectively, using available source data.
4. Inadequate response to treatment with oral, SC, or intramuscular (IM) MTX (see Section 5.1 for definition of inadequate response to MTX treatment) for at least 12 weeks prior to Screening at a dose of 15 to 25 mg/week (or ≥ 10 mg/week if intolerant to higher doses)
 - The dose and means of administering MTX must have been stable for at least 6 weeks prior to Screening.
5. Subjects must be willing to take folic acid or equivalent throughout the study.
6. Subjects must have moderately to severely active RA disease as defined by all of the following:

- a. ≥ 6 tender joints (68-joint count) at Screening and baseline; and
- b. ≥ 6 swollen joints (66-joint count) at Screening and baseline; and
- c. CRP above ULN at Screening based on the central laboratory results.

5.3.2 Exclusion Criteria

Subjects who meet any of the following criteria will not be eligible for the study:

1. Diagnosis of any other inflammatory arthritis or systemic rheumatic disease (e.g., gout, psoriatic or reactive arthritis, Crohn's disease, Lyme disease, juvenile idiopathic arthritis, or systemic lupus erythematosus)
 - However, subjects may have secondary Sjogren's syndrome or hypothyroidism
2. Subjects who are Steinbrocker class IV functional capacity (incapacitated, largely or wholly bed-ridden or confined to a wheelchair, with little or no self-care) (see Appendix 1 [Section 13.1])
3. Prior exposure to any licensed or investigational compound directly or indirectly targeting IL-6 or IL-6R (including tofacitinib or other Janus kinases and spleen tyrosine kinase [SYK] inhibitors)
4. Prior treatment with cell-depleting therapies, including anti-CD20 or investigational agents (e.g., CAMPATH, anti-CD4, anti-CD5, anti-CD3, and anti-CD19)
5. Prior use of bDMARDs, with the following exception:
 - Subjects who discontinued TNFi therapy due to a reason other than lack of efficacy are allowed to enter the study (TNFi therapy should not be discontinued to facilitate a subject's participation in the study, but should instead have been previously discontinued as part of a subject's medical management of RA). The use of TNFi therapy within the following windows prior to baseline is exclusionary:
 - a. 4 weeks for etanercept
 - b. 8 weeks for infliximab
 - c. 10 weeks for adalimumab, certolizumab, and golimumab
6. Use of parenteral and/or intra-articular glucocorticoids within 4 weeks prior to baseline
7. Use of oral glucocorticoids greater than 10 mg/day prednisone (or equivalent), or change in dosage within 2 weeks prior to baseline

8. Prior documented history of no response to hydroxychloroquine and sulfasalazine
9. Prior use of cDMARDs (other than MTX) within the following windows prior to baseline (cDMARDs should not be discontinued to facilitate a subject's participation in the study, but should instead have been previously discontinued as part of a subject's medical management of RA):
 - a. 4 weeks for sulfasalazine, azathioprine, cyclosporine, hydroxychloroquine, chloroquine, gold, penicillamine, minocycline, or doxycycline
 - b. 12 weeks for leflunomide unless the subject has completed the following elimination procedure at least 4 weeks prior to baseline: Cholestyramine at a dosage of 8 grams 3 times daily for at least 24 hours, or activated charcoal at a dosage of 50 grams 4 times daily for at least 24 hours
 - c. 24 weeks for cyclophosphamide
10. Vaccination with live vaccines in the 6 weeks prior to baseline or planned vaccination with live vaccines during the study
11. Participation in any other investigational drug study within 30 days or 5 times the terminal half-life of the investigational drug, whichever is longer, prior to baseline
12. Other treatments for RA (e.g., Prosurba Device/Column) within 6 months prior to baseline
13. Use of intra-articular hyaluronic acid injections within 4 weeks prior to baseline
14. Use of non-steroidal anti-inflammatory drugs (NSAIDs) on unstable dose or switching of NSAIDs within 2 weeks prior to baseline
15. Previous participation in this study (randomized) or another study of OKZ
16. Abnormal laboratory values, as defined below:
 - a. Creatinine level ≥ 1.5 mg/dL (132 $\mu\text{mol/L}$) for females or ≥ 2.0 mg/dL (177 $\mu\text{mol/L}$) for males
 - b. ALT or AST level $\geq 1.5 \times$ ULN
 - c. Platelets $< 100 \times 10^9/\text{L}$ ($< 100,000/\text{mm}^3$)
 - d. White blood cell count $< 3.5 \times 10^9/\text{L}$
 - e. Neutrophil count $< 2000 \times 10^6/\text{L}$ ($< 2000/\text{mm}^3$)

- f. Hemoglobin level ≤ 80 g/L
 - g. Glycosylated hemoglobin (HbA_{1c}) level $\geq 8\%$
17. Subjects with concurrent acute or chronic viral hepatitis B or C infection as detected by blood tests at Screening (e.g., positive for hepatitis B surface antigen [HBsAg], total hepatitis B core antibody [anti-HBc], or hepatitis C virus antibody [HCV Ab])
- a. Subjects who are positive for hepatitis B surface antibody (anti-HBs), but negative for HBsAg and anti-HBc, will be eligible.
18. Subjects with HIV infection
19. Subjects with:
- a. Suspected or confirmed current active TB disease or a history of active TB disease
 - b. Close contact (i.e., sharing the same household or other enclosed environment, such as a social gathering place, workplace, or facility, for extended periods during the day) with an individual with active TB within 1.5 years prior to Screening
 - c. History of untreated latent TB infection (LTBI), regardless of IGRA result at Screening
 - i. Subjects with a history of untreated LTBI may be re-screened and enrolled if they fulfill all 3 of the following criteria:
 - 1. Active TB is ruled out by a certified TB specialist or pulmonologist who is familiar with diagnosing and treating TB (as acceptable per local practice);
 - 2. The subject has completed at least 30 days of LTBI-appropriate prophylaxis prior to baseline with agents recommended as preventative therapy for LTBI according to country-specific/Centers for Disease Control and Prevention (CDC) guidelines (see Appendix 7 [Section 13.7]) (treatment with isoniazid for 6 months is not an appropriate prophylactic regime for this study and it should not be used); and
 - 3. The subject is willing to complete the entire course of recommended LTBI therapy (see Appendix 7 [Section 13.7]).

- d. Positive interferon-gamma release assay (IGRA) result at Screening. If indeterminate, the IGRA can be repeated once during the Screening Period. If there is a second indeterminate result, the subject will be excluded.
 - i. Subjects with a positive IGRA result at Screening may be re-screened and enrolled if they fulfill all 3 of the following criteria:
 1. Active TB is ruled out by a certified TB specialist or pulmonologist who is familiar with diagnosing and treating TB (as acceptable per local practice);
 2. The subject has completed at least 30 days of LTBI-appropriate prophylaxis prior to baseline with agents recommended as preventative therapy for LTBI according to country-specific/CDC guidelines (see Appendix 7 [Section 13.7]) (treatment with isoniazid for 6 months is not an appropriate prophylactic regime for this study and it should not be used); and
 3. The subject is willing to complete the entire course of recommended LTBI therapy (see Appendix 7 [Section 13.7]).
 - ii. If a subject with a positive IGRA result at Screening has documented evidence of completing treatment for LTBI with a treatment regime and treatment duration that are appropriate for this study, the subject may be enrolled without further prophylaxis if recommended by a certified TB specialist or pulmonologist who is familiar with diagnosing and treating TB (as acceptable per local practice) and no new exposure in close contact with an individual with active TB after completing the prophylactic treatment is suspected.
20. Concurrent malignancy or a history of malignancy within the last 5 years (with the exception of successfully treated carcinoma of the cervix in situ and successfully treated basal cell carcinoma and squamous cell carcinoma not less than 1 year prior to Screening [and no more than 3 excised skin cancers within the last 5 years prior to Screening])
21. Subjects with any of the following CV conditions:
- a. Uncompensated congestive heart failure, or class III or IV heart failure defined by the New York Heart Association classification (The Criteria Committee of the New York Heart Association, 1994) as noted in Appendix 2 (see Section 13.2)
 - b. Untreated or resistant arterial hypertension Grade II-III (systolic blood pressure [BP] >160 mm Hg and/or diastolic BP >100 mm Hg)
 - c. History or presence of concurrent severe and/or uncontrolled CV disorder (including but not limited to acute coronary syndrome or stroke/transient ischemic attack in the

previous 3 months before Screening) that would, in the Investigator's judgment, contraindicate subject participation in the clinical study, or clinically significant enough in the opinion of the Investigator to alter the disposition of the study treatment, or constitute a possible confounding factor for assessment of efficacy or safety of the study treatment

22. Subjects with a history or presence of any concurrent severe and/or uncontrolled medical condition (including but not limited to respiratory, hepatic, renal, GI, endocrinological, dermatological, neurological, psychiatric, hematological [including bleeding disorder], or immunologic/immunodeficiency disorder[s]) that would, in the Investigator's judgment, contraindicate subject participation in the clinical study, or clinically significant enough in the opinion of the Investigator to alter the disposition of the study treatment, or constitute a possible confounding factor for assessment of efficacy or safety of the study treatment
23. Uncontrolled diabetes mellitus
24. Subjects with any infection requiring oral antibiotic or antiviral therapy in the 2 weeks prior to Screening or at baseline, injectable anti-infective therapy in the last 4 weeks prior to baseline, or serious or recurrent infection with history of hospitalization in the 6 months prior to baseline
25. Subjects with evidence of disseminated herpes zoster infection, zoster encephalitis, meningitis, or other non-self-limited herpes zoster infections in the 6 months prior to baseline
26. Subjects with planned surgery during the study or surgery ≤ 4 weeks prior to Screening and from which the subject has not fully recovered, as judged by the Investigator
27. Subjects with diverticulitis or other symptomatic GI conditions that might predispose the subject to perforations, including subjects with a history of such predisposing conditions (e.g., diverticulitis, GI perforation, or ulcerative colitis)
28. Pre-existing central nervous system demyelinating disorders (e.g., multiple sclerosis and optic neuritis)
29. History of chronic alcohol or drug abuse as judged by the Investigator
30. Female subjects who are pregnant, currently lactating, have lactated within the last 12 weeks, or who are planning to become pregnant during the study or within 6 months of last dose of study treatment

31. Female subjects of childbearing potential (unless permanent cessation of menstrual periods, determined retrospectively after a woman has experienced 12 months of natural amenorrhea as defined by the amenorrhea with underlying status [e.g., correlative age] or 6 months of natural amenorrhea with documented serum follicle-stimulating hormone levels >40 mIU/mL and estradiol <20 pg/mL) who are not willing to use a highly effective method of contraception during the study and for at least 6 months after the last administration of study treatment

OR

Male subjects with partners of childbearing potential not willing to use a highly effective method of contraception during the study and for at least 3 months after the last administration of study treatment

Highly effective contraception is defined as:

- Female sterilization surgery: hysterectomy, surgical bilateral oophorectomy (with or without hysterectomy), or tubal ligation at least 6 weeks prior to the first dose of study treatment
 - In the case of oophorectomy alone, only when the reproductive status of the woman has been confirmed by documented follow-up hormone level assessment
- Total abstinence if it is the preferred and constant lifestyle of the subject. Thus, periodic abstinence such as ovulation, symptothermal, postovulation, calendar methods, and withdrawal are not acceptable methods of contraception.
- Male sterilization surgery: at least 6 months prior to Screening (with the appropriate postvasectomy documentation of the absence of sperm in the ejaculate). For female subjects, the vasectomized male should be the only partner.
- Placement of established intrauterine device (IUD): IUD copper or IUD with progesterone
- Barrier method (condom and intravaginal spermicide, cervical caps with spermicide, diaphragm with spermicide) in combination with the following: established oral, injected, or implanted hormone methods of contraception or contraceptive patch

32. Subjects with a known hypersensitivity to any component of the OKZ drug product or placebo

33. Subjects with a known hypersensitivity or contraindication to any component of the rescue medication (see Section 6.13.3)

34. History of severe allergic or anaphylactic reactions to human, humanized, or murine monoclonal antibodies
35. Subject's unwillingness or inability to follow the procedures outlined in the protocol
36. Other medical or psychiatric conditions or laboratory abnormalities that may increase potential risk associated with study participation and administration of investigational products, or that may affect study results interpretation and, as per the Investigator's judgment, make the subject ineligible

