5.4.1 Double-blind Period: Visit 1 (Screening) through Visit 15 (Week 24)

5.4.1.1 Screening (Visit 1, Days -28 to -1)

A separate ICF is completed for the main study, PK subpopulation (optional), and PG study (optional). Written informed consent must be obtained prior to the performance of any protocol-specific procedures at Screening, including the discontinuation of any prohibited medications. The Investigator at each study site will ensure that each subject has been provided with full and adequate oral and written information about the nature, purpose, and available details of possible risks and benefits of the study.

Subjects must also be notified that they are free to discontinue from the study treatment or the whole study at any time. The Investigator will discuss with the subject the importance of participation in the study despite the discontinuation of study treatment. The subject should be given the opportunity to ask questions and allowed adequate time to consider the written information provided. The Investigator must retain the original, signed ICF for the study file. A copy of the signed ICF must be given to the subject. Once informed consent has been obtained, the subject's eligibility to enter the study will be verified in accordance with the inclusion and exclusion criteria (refer to Sections 5.3.1 and 5.3.2, respectively).

Enrollment will occur using an IWRS at Screening upon ICF signature. The IWRS will assign a unique subject number at Screening.

Screening may be conducted up to 28 days prior to randomization.

If the Investigator considers Screening laboratory tests with exclusionary results to be due to laboratory error or a transient condition, these tests may be repeated once during the Screening Period for confirmation. In addition, the CRP test can be repeated once during the Screening Period to assess eligibility, provided that the results arrive prior to the randomization date. No extensions of the Screening Period will be granted for missing laboratory data unless this is due to a central laboratory error.

Screen failure and re-screening are discussed in Section 5.4.4.

In addition to obtaining subject informed consent, the following assessments will be performed at Screening:

- Assign subject number via IWRS.
- Check eligibility criteria, including documenting of tender joints and diagnosis of RA.
- Record subject demographics.
- Record medical history.
- Record details of contraceptive history/status.

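### Exclusion 24 leaves the Screening Period itself uncovered for orally treated infection, although its other two limbs run back from baseline

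*Combined protocol and SAP*

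**What the plan says.** Exclusion 24 in Section 5.3.2 has three limbs:

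- Oral treatment: "Subjects with any infection requiring oral antibiotic or antiviral therapy in the 2 weeks prior to Screening or at baseline".
- Injectable treatment: "injectable anti-infective therapy in the last 4 weeks prior to baseline".
- More severe disease: "serious or recurrent infection with history of hospitalization in the 6 months prior to baseline".

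The second and third count back from baseline. The first counts back from Screening and then applies again only on the baseline day.

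Section 5.4.1.1 sets the distance between those two points: "Screening may be conducted up to 28 days prior to randomization".

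Inclusion 6 in Section 5.3.1 treats its components differently. The laboratory component is "CRP above ULN at Screening based on the central laboratory results", with no baseline requirement. The joint counts must be met twice, for example at least 6 "swollen joints (66-joint count) at Screening and baseline". Section 5.4.1.1 also says that "the CRP test can be repeated once during the Screening Period to assess eligibility, provided that the results arrive prior to the randomization date". No condition about infection is attached to that repeat. Other exclusionary laboratory results may be repeated only if the Investigator suspects laboratory error or a transient condition.

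**The concern.** The interval closest to the first dose is the one that the oral limb leaves open. Older treatment excludes a subject and more recent treatment does not, which is hard to square with a criterion meant to keep recently infected subjects off study treatment. Most drug washouts in the same list (exclusions 5 to 7 and 9 to 14) count from baseline, so this looks like a drafting slip.

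Safety is the main stake. Section 7.6.3 lists infections as an adverse event of special interest. Section 7.6.3.1 warns that suppression of the acute phase reaction can mask signs of infection. Section 5.2.2 gives a half-life of about 31 days, so exposure does not end quickly if an incompletely treated infection returns after the first injection.

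The second stake is the study population. A raised CRP at entry may reflect an intercurrent infection rather than rheumatoid inflammation, and CRP is not re-tested against the criterion at baseline.

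**Working it through.** The plan states no figure on this point, so there is none to reproduce. The check is a count of days, followed by a reading of the other safeguards.

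**Inputs.** Baseline is Day 0 and the Screening visit is on Day s. From exclusion 24, the oral limb covers Days s-14 to s-1 plus Day 0, and the injectable limb covers Days -28 to 0. From 5.4.1.1, s lies between -28 and -1.

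**Screening days (Day s to Day -1) not covered**

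| Screening visit | Oral look-back | Oral limb: uncovered | Injectable limb: uncovered |
|---|---|---|---|
| Day -28 | Days -42 to -29 | 28 | 0 |
| Day -21 | Days -35 to -22 | 21 | 0 |
| Day -14 | Days -28 to -15 | 14 | 0 |
| Day -7 | Days -21 to -8 | 7 | 0 |
| Day -1 | Days -15 to -2 | 1 | 0 |

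The oral limb never covers a Screening day; the injectable limb covers all of them.

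**Two subjects, both screened on Day -28.** One finishes a short oral course on Day -41. Since -28 - 13 = -41, this lies inside Days -42 to -29 and the subject is excluded. The other takes oral treatment from Day -20 to Day -1. No treated day falls in Days -42 to -29 or on Day 0, so the criterion is not met.

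**Other safeguards.** Exclusion 22 requires a severe or uncontrolled condition and the Investigator's judgment. Exclusion 36 also rests on judgment. Section 6.11.1 withholds dosing when an infection is active or clinically significant. No numbered criterion expressly covers a non-serious, orally treated infection that begins and ends within Screening.

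**CRP route.** Inclusion 6c can be met in two ways: the first CRP is drawn during an infection whose oral treatment starts at or after the Screening visit, or a normal first CRP is followed by a raised repeat during infection.

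**Numbers affected.** The documents give no infection rate. If 2%, 5% or 8% of subjects took an oral anti-infective during Screening (assumption): 0.02 x 420 = 8.4, 0.05 x 420 = 21, 0.08 x 420 = 33.6, or about 8, 21 and 34. Each is an upper bound at its rate, because it assumes a full 28-day Screening Period and removes neither courses still running at baseline, nor injectable or hospitalized cases, nor subjects excluded by judgment.

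**Efficacy.** Section 9.4 takes baseline as the last assessment before first dose, so the Visit 2 CRP enters the analysis, not the Screening value or its repeat. If that value were still raised and later fell from 30 to 5 mg/L (assumed values), the CRP term in Section 7.1.6 would fall by 0.36 x [ln(31) - ln(6)] = 0.36 x (3.434 - 1.792) = 0.59, with joints unchanged. This bears on DAS28 (CRP) change, which Section 4.3 lists among the other endpoints.

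**The case against.** **The subject is not unprotected.** A reader might infer that a just-treated subject passes into the trial unseen. The documents do not support that. Adverse events are recorded from consent. Visit 2 includes an eligibility review, concomitant medications, a complete physical examination and vital signs. An Investigator can act under exclusion 36, and 6.11.1 extends to clinically significant infections as well as active ones. This stands, but the protection is discretionary and can differ between sites, whereas the other two limbs are fixed rules.

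**The efficacy results are not materially at risk.** A reader might infer that infection-raised CRP inflates placebo response and dilutes the treatment contrast. The endpoint definitions largely rule this out. ACR20 requires improvement in both joint counts plus three of five further measures, of which CRP is one, so a CRP fall alone cannot make a responder. DAS28 (CRP) below 3.2 is an absolute threshold, which a high starting CRP makes no easier to reach. HAQ-DI and CDAI contain no CRP. If the infection has resolved by Visit 2, the CRP component has less room to improve, not more.

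**CRP is not the sole evidence of inflammation.** At least 6 swollen joints, counted by an independent assessor, are required at both Screening and baseline. That limits the population argument considerably.

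**The wording might be read more generously.** It could be taken as two weeks before Screening or two weeks before baseline. The word at, placed before baseline, does not say so, and on that reading Days -28 to -15 of a full-length Screening Period would still be open.

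**Anchoring to Screening is not unique.** Exclusions 19b, 21c and 26 also use it. That is correct, but it does not explain a split of anchors among limbs of one criterion that address the same hazard.

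**Conclusion.** The concern holds as an internal inconsistency in exclusion 24. Between 1 and 28 days immediately before baseline are uncovered for oral treatment, depending on the length of Screening, and none are uncovered for injectable treatment. This rests on the literal wording and on a course that has ended by baseline without injectable therapy or a qualifying hospitalization.

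The grounds are mainly safety. Entry on an infection-raised CRP is possible but secondary, since the joint-count criteria must still be met twice. Any efficacy effect is small and needs CRP to be still raised at Visit 2. The gap precedes randomization and applies equally to all arms, so it does not affect type I error. The number affected is unknown; 8 to 34 of 420 is an upper bound at assumed rates of 2% to 8%. This is a cheap correction worth making, not a threat to the trial's conclusions.

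**What to change.** Reconcile the three limbs of exclusion 24 so that the oral look-back runs without a break through the Screening Period up to and including baseline. The length of the window is for the sponsor to set.

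State an explicit exception for latent tuberculosis prophylaxis. Exclusion 19 admits subjects who have had at least 30 days of it before baseline and will complete the course. Read literally, the oral limb already sits uneasily with that route on the baseline day, and a continuous window without an exception would widen the conflict.

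A separate sentence on the CRP repeat is then largely unnecessary, because a subject treated orally during Screening would already be excluded. Affected subjects can use re-screening under Section 5.4.4, which repeats the Screening assessments, including CRP.

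The cost is one rephrased criterion and a small number of subjects delayed or re-screened. No new data are needed, since adverse events and concomitant medications are already recorded from Screening and eligibility is reviewed at Visit 2.
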